**Table 3-2 Study VX15-770-123: Part 1 and Part 2**

		Part 1 Placebo-controlled Crossover Period a																
		Treatment Period 1 (Day 1 to Wk 8)				Treatment Period 2 (Wk 16 to Wk 24)				Part 2 Open-label Period a (Wk 24 to Wk 144)								
		Wk 4 (± 3 days)	Wk 8 (± 5 days)	8 Wks (± 5 days)	Wash- out	Wk 16 (± 3 days)	Wk 20 (± 3 days)	Wk 24 (± 5 days)	Wk 36 (± 2 wks)	Wk 48 (± 2 wks)	Wk 60 (± 2 wks)	Wk 72 (± 2 wks)	Wk 84 (± 2 wks)	Wk 96 (± 2 wks)	Wk 108 (± 2 wks)	Wk 120 (± 2 wks)	Wk 132 (± 2 wks)	Wk 144 (± 2 wks)
Event/ Assessment	Day 1	X	X	X	X	X	X	X	X	X	X	X	X	X	X	X	X	X
Clinic visit		X	X			X	X	X	X	X	X	X	X	X	X	X	X	X
Inclusion/exclusion criteria review		X																
Randomization b		X																
Concomitant medications		X	X			X	X	X	X	X	X	X	X	X	X	X	X	X
Concomitant treatments and procedures		X	X			X	X	X	X	X	X	X	X	X	X	X	X	X
Height and weight		X				X	X	X	X	X	X	X	X	X	X	X	X	X
Multiple breath washout c		X	X			X	X	X	X	X	X	X	X	X	X	X	X	X

Notes: Subjects may complete their assessments over a period of 2 days at the Day 1 and Week 96 Visits. On the Day 1, Week 16, and Week 24 Visits, all assessments must be completed before dosing with study drug. Symptom-directed physical examinations and symptom-directed vital signs can be performed if deemed necessary by the investigator or healthcare provider (see Section 11.5.3).

a Subjects who prematurely discontinue study drug treatment (for any reason other than early study termination) will undergo the listed assessments at their Early Termination of Treatment Visit (see Table 3-3), which is to be scheduled as soon as possible after the subject decides to terminate study drug treatment. Subjects who prematurely discontinue treatment will also be required to complete the Safety Follow-up Visit, approximately 4 weeks (± 7 days) after their last dose of study drug. If the Early Termination of Treatment Visit occurs 3 weeks or later following the last dose of study drug, then the Early Termination of Treatment Visit will replace the Safety Follow-up Visit, and a separate Safety Follow-up Visit will not be required (see Section 8.1.7).

[figure not shown]

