#### **8.1.4 Part 1: Treatment Period 2 (8 Weeks)**

The first dose of study drug in Treatment Period 2 will be administered at the Week 16 Visit after completing the Week 16 assessments. Study drug should be taken according to instructions provided. In order to continue into Treatment Period 2, subjects must not have an acute upper or lower respiratory infection, pulmonary exacerbation, or changes in therapy (including antibiotics) for pulmonary disease within 4 weeks before the Week 16 Visit (first dose of study drug in Treatment Period 2) and must not have any “non-CF-related” illness within 2 weeks before the Week 16 Visit (first dose of study drug in Treatment Period 2). “Illness” is defined as an acute (serious or non-serious) condition (e.g., gastroenteritis). If the subject does not meet these criteria, then the continuation of the subject into Treatment Period 2 should be discussed with the Vertex medical monitor. The last dose of study drug in Treatment Period 2 is the dose of study drug before the planned Week 24 Visit. Study visits will occur on Weeks 16, 20, and 24.

Following a review of study enrollment and assessment of the available number of potential subjects for this study, Vertex decided to close enrollment and terminate the study early. After the protocol amendment has been approved at a site, subjects in Part 1 will be withdrawn from the study at their Week 24 Visit (see [Section 8.1](#)).

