## **10.2 Administration**

During Part 1, each 50- or 75-mg dose of ivacaftor will be provided as granules in a capsule. During Part 2, these doses will be provided as granules in a sachet.

The entire contents of each capsule or sachet of granules should be mixed with 1 teaspoon (5 mL) of age-appropriate soft food or liquid and completely consumed. Each dose should be administered just before or just after fat-containing food. Parents will be instructed on how to empty the capsules or sachets and administer ivacaftor with food. Details of dose preparation and dose administration will be provided in the Study Manual.

The 150-mg dose of ivacaftor will be provided as two 75-mg doses of ivacaftor in sachets. The 150-mg dose may also be provided as a tablet after discussion with the medical monitor. It is recommended that subjects take 150-mg dose of ivacaftor with fat-containing food. Examples of appropriate fat-containing foods will be described in the Study Manual.

Guidelines for ivacaftor administration are as follows:

- Ivacaftor should be administered q12h.
- Whenever possible, subjects should take ivacaftor at the same time each day. For example, the morning dose could be taken at 8:00 AM every morning and the evening dose could be taken at 8:00 PM every evening throughout the study.
- If subjects forget to take a dose and remember within 0 to 6 hours (before the halfway point of the dosing interval), they should take the dose at that time with fat-containing food and resume their normal schedule for the following dose.

- If subjects forget to take a dose and remember within 6 to 12 hours after the missed dose, they should skip that dose and resume their normal schedule for the following dose.

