**Treatment Emergent (TE) Period:**

- For Treatment Period 1 of Part 1, the TE period will be from the first dose of study drug in Treatment Period 1 of Part 1 to the earliest of the following:
  - 1) 28 days after the date of subject's treatment completion during Treatment Period 1
  - 2) Safety Follow-up Visit if discontinued study early during Treatment Period 1
  - 3) 28 days after the last dose of the study drug for subjects who discontinued the study early during Treatment Period 1 and do not have a Safety Follow-up Visit
- For Treatment Period 2 of Part 1, the TE period will be from the first dose of study drug in the Treatment Period 2 of Part 1 to the earliest of the following:
  - 1) The date of treatment completion of Treatment Period 2
  - 2) Safety Follow-up Visit if discontinued study early during Treatment Period 2
  - 3) 28 days after the last dose of the study drug for subjects who discontinued the study early during Treatment Period 1 and do not have a Safety Follow-up Visit
- For Part 2, the TE period will be from the first dose of study drug in Part 2 to the earliest of the following:
  - 1) The Safety Follow-up Visit,
  - 2) 28 days after the last dose of the study drug for subjects who discontinued the study during Part 2 and do not have a Safety Follow-up Visit,

**Visit Windowing Rules:** Appendix C defines the windows for protocol-defined visits. The windows will be applied using the following rules for both scheduled and unscheduled visits. If no measurement is available within a visit window, the assessment will be considered missing for the visit. If there is more than one measurement available within the same visit window, the following rules will be used:

- For all safety parameters, if there are multiple measurements within a visit window, then 1) the record closest to the target day will be used, with the exception of the threshold analysis in which the worst record will be used; 2) if there are multiple records within the same distance of the target day, the latest record will be used; or 3) the Safety Follow-Up (SFU) visit will not be windowed; instead, the nominal visit will be used in relevant analyses.
- For all efficacy parameters, if there are multiple measurements within a visit window, the record at the scheduled visit will be used. Otherwise,
  - If there are no measurements at the scheduled visit, then the record closest to the target day will be used;

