### 9.4.1 Adverse Events

For analysis purposes, adverse events will be classified as pre-treatment emergent, TEAE, or post-treatment emergent. Adverse events which start (or increase in severity) during the period from the signing of informed consent up to, but not including, the first dose of study drug will be considered pre-treatment. Adverse events which start (or increase in severity) during the period from the first dose of study drug through completion of the Follow-up Visit will be considered TEAE. Adverse events which start (or increase in severity) after the completion of the Follow-up Visit will be considered post-treatment adverse events.

If an adverse event started (or increased in severity) during a specific treatment period, this adverse event will be attributed to the study drug the subject is receiving during this Treatment Period. Adverse events that started (or increased in severity) during the Washout Period and within 28 days of the last dose of treatment period 1 will be attributed to the treatment received in Treatment Period 1. Please see Section 9.1 for details.

For determining whether the AEs with missing or partially missing dates are treatment-emergent, please refer to Appendix D for rules. Please note that no imputation will be displayed in the listing outputs.

Adverse event summary tables will be presented for TEAE only and will include the following:

All TEAEs,

Related (defined as possibly related or related) TEAEs,

TEAEs leading to treatment discontinuation,

Serious TEAEs,

TEAEs by severity,

TEAEs by relationship.

Summaries will be presented by MedDRA system organ class and preferred term using frequency counts and percentages (i.e., number and percentage of subjects with an event). Subjects with multiple occurrences of the same adverse event or a continuing adverse event will be counted once, and only the maximum severity level will be presented in the severity summaries, and the worst/highest relationship level in the relationship summaries. In addition,

listing containing individual subject adverse event data for all deaths and other serious and significant adverse events will be provided, separately. All adverse events including Pre- and Post-treatment adverse events will be presented in individual subject data listings.

Imputation rules for missing or partial AE dates are presented in Appendix D.

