#### **9.4.2 Clinical Laboratory**

The following analyses for the lab assessments will be presented:

- Post-baseline values and change from baseline for chemistry, hematology, and LFT results will be summarized using SI units by treatment group at each scheduled time point.
- Abnormal hematology, chemistry, and LFT results will be summarized at each visit and also listed. Both abnormal low and high will be presented for hematology and chemistry results. Only abnormal high (elevated LFT) will be presented for LFT results.
- Number and percentage of subjects with abnormal LFT results meeting the threshold criteria will be summarized by treatment group at each scheduled time point. The threshold criteria for abnormal are provided in Appendix E. Results will also be presented overall by treatment group.
- The shift incidence of LFT results meeting threshold criteria against the baseline threshold criteria will be summarized by treatment group at each scheduled time point (only shifts to values worse than baseline will be presented).
- Box plots for the Ratio of LFT results to the ULN will be plotted against visit for each treatment group.
- Mean values ( $\pm$ SD) will be plotted against visit for ALT, AST, ALP, total bilirubin, and GGT for each treatment group.
- A scatterplot based on multiples of ULN will be provided for peak ALT versus peak total bilirubin and peak AST versus peak total bilirubin during the TE Period for each treatment group.
- Results of urinalysis and coagulation studies (only collected at screening) will be listed in individual subject data listings.

LFT includes ALT, AST, ALP, total bilirubin, and GGT. When presenting data for ALT and AST and additional category for ALT/AST (ALT or AST) will be presented.

Threshold analysis criteria for LFTs are presented in Appendix E.

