## Appendix C: Visit Window Mapping Rules for Efficacy and Safety Measurements

*Table 10-4 Visit Window Mapping Rules (within Period)*

Assessments	Period - Visit	Analysis Visit	Target Study Day	Visit Window (in study days)

 
• Labs               
 
○ Chemistry
 
○ Hematology
 
○ Liver Function Tests
 
○ Weight, Height.
 
 
 
	1 - Day 1	Day 1	1	[1, 1]
	1 - Week 8	Week 8	57	[2, 85]
	2 - Week 16	Day 1	1	[1, 1]
	2 - Week 24	Week 8	57	[2, Date of Week 24 visit]
	2 – Safety Follow-up Visit	Safety Follow-up Visit	NA	Use the nominal visit name

 
• LCI
 
	1 - Day 1	Day 1	1	[1, 1]
	1 - Week 4	Week 4	28	[2, 42 ]
	1 - Week 8	Week 8	57	[43, 85]
	2 - Week 16	Day 1	1	[1, 1]
	2 - Week 20	Week 4	28	[2, 42 ]
	2 - Week 24	Week 8	57	[43, Date of Week 24 visit]
	2 – Safety Follow-up Visit	Safety Follow-up Visit	NA	Use the nominal visit name

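### SAP 9.1 ends the Period 2 treatment-emergent period on an undefined completion date with no tail, so Week 24 liver tests can be misplaced and later repeat tests in withdrawn children do not count, unlike in Period 1.

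*SAP*

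**What the plan says.** SAP 9.1 (Treatment Emergent Period) defines each TE period as ending at the earliest of several dates. For a child who completes the period, the governing date in Period 1 is "28 days after the date of subject's treatment completion during Treatment Period 1". In Period 2 it is "The date of treatment completion of Treatment Period 2". The Part 2 TE period begins with the first Part 2 dose. Treatment completion is not defined as either the last dose or the visit.

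SAP 9.4.2 calls for scatterplots of "peak ALT versus peak total bilirubin and peak AST versus peak total bilirubin during the TE Period for each treatment group". Among the laboratory outputs, only these plots are explicitly restricted to the TE period.

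On timing, Protocol 8.1.4 states: "The last dose of study drug in Treatment Period 2 is the dose of study drug before the planned Week 24 Visit". The notes to Protocol Table 3-2 add: "On the Day 1, Week 16, and Week 24 Visits, all assessments must be completed before dosing with study drug". The Week 24 blood sample therefore follows the last Period 2 dose and precedes any Part 2 dose.

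SAP Appendix C gives laboratory values a Period 1 window of Day 2 to Day 85 (target Day 57). The Period 2 window has the bounds "2, Date of Week 24 visit". In Period 2 it maps one pre-dose laboratory visit (Week 16) and one post-dose visit (Week 24), plus a nominal Safety Follow-up Visit.

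Protocol 8.1 now withdraws Part 1 children at Week 24 once a site has approved the amendment, and asks for no Safety Follow-up Visit from children withdrawn because the study is ending.

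**The concern.** Ending the Period 2 TE period without a tail makes sense for a child who starts open-label ivacaftor at Week 24, because a tail would overlap Part 2. It does not suit a child withdrawn at Week 24, who has no Part 2 dose to overlap, and the rule has no branch for that child.

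Two things are at stake. First, the scatterplots look for transaminase and bilirubin peaks in the same child. If the Week 24 sample lies outside the TE period, the plots lose the end-of-ivacaftor value for Sequence 2 and the end-of-placebo value for Sequence 1, while the by-visit tables keep both. Second, a child with a raised result may have it repeated. Protocol 11.5.2 recommends confirmation within 48 to 72 hours for certain new transaminase elevations with symptoms. A repeat soon after Week 8 can set the Period 1 peak. The same repeat after Week 24 cannot set the Period 2 peak.

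**Working it through.** **Inputs.** Week 8 and Week 24 laboratory target: Day 57 within the period (Appendix C). Visit window: ±5 days (Table 3-2). Period 1 tail: 28 days; Period 2 tail: none (SAP 9.1). Dosing is every 12 hours. Protocol 10.2 gives as an example that "the morning dose could be taken at 8:00 AM every morning and the evening dose could be taken at 8:00 PM every evening", so the last dose before a visit may fall on the previous evening or on the same morning.

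**The plan's own figure.** The Period 1 laboratory window ends on Day 85. Counting the tail from the visit gives 57 + 28 = 85, an exact match. Counting it from a last dose on Day 56 gives 56 + 28 = 84.

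**TE end under each reading, visit on Day 57.**

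| Reading of completion | Period 1 TE end | Week 8 test | Period 2 TE end | Week 24 test |
|---|---|---|---|---|
| Last-dose date, dose the evening before | 56 + 28 = 84 | 57 ≤ 84, in | 56 | 57 > 56, out |
| Last-dose date, dose the same morning | 57 + 28 = 85 | in | 57 | in |
| Visit date | 57 + 28 = 85 | in | 57 | in |

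Moving the visit within its window does not change the first row. For a visit on Day 52, Period 1 ends on Day 79 and Period 2 on Day 51; for Day 62, on Day 89 and Day 61. The Week 8 test is in and the Week 24 test is out each time.

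**Children entering Part 2.** Their first Part 2 dose is given at the Week 24 Visit, so it carries the sample's date. If only dates are compared, the Week 24 test meets the Part 2 TE start under every reading. Under the second and third rows it is then in both periods; under the first row it is in Part 2 only. If times are compared, the first row leaves it in no TE period. A Sequence 1 child's end-of-placebo value could thus be shown under ivacaftor. Since SAP 9.4 draws safety data from Part 1, this arises only if Part 2 records are added to the ivacaftor group.

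**Unscheduled repeat three days after the visit (Day 60).** Period 1: 60 ≤ 84, so it is in the TE period on every reading and also inside the Day 2 to 85 window. Period 2, child withdrawn at Week 24: 60 > 57, so it is outside the TE period on every reading and outside the Appendix C window. The threshold analysis takes the worst record in the window (SAP 9.1), so it has the same gap.

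**Observation time.** Period 1: about 56 + 28 = 84 days. Period 2: about 56 + 0 = 56 days.

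**Which reading does the SAP support?** SAP 9.4.1 restates the Period 1 rule for adverse events as "within 28 days of the last dose of treatment period 1 will be attributed to the treatment received in Treatment Period 1", which points to the last dose. Appendix C, by the 85-day match and by closing Period 2 on the visit date, points to the visit. Each reading has support in the text.

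**The case against.** The strongest reply is that the visit-date reading fits better. SAP 9.1 uses last dose for early discontinuers and treatment completion for completers within the same list, which suggests two different dates. Appendix C agrees to the day, and the 9.4.1 sentence concerns washout adverse events and refers back to 9.1. On that reading the Week 24 tests stay in the plots. This stands as far as it goes: exclusion of the Week 24 tests is possible, not shown. But Day 85 is a visit-window limit, not a definition of the TE period, and two programmers could defensibly produce different plots.

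A second reply is that little is lost. By-visit summaries, threshold and shift tables, box plots and listings keep Week 24, and Appendix E has combined transaminase and bilirubin criteria, so a combined elevation at Week 24 would still be tabulated. Appendix C maps no laboratory visit between Week 8 and Week 16, so the Period 1 tail adds only unscheduled tests. All of this stands and limits the point.

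A reader might go further and infer that the Week 24 liver tests are definitely excluded, that each treatment's plot rests on half the children, or that the SAP's main liver-injury display is compromised. The documents do not support this. The first needs both the last-dose reading and an earlier calendar day for that dose. The second also needs there to be no Week 20 sample, which the damaged columns of Table 3-2 cannot settle, although Appendix C maps none. As to the third, neither document ranks the scatterplots above the other liver outputs.

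**Conclusion.** The point holds in a limited form. Under any reading, the rule follows the two periods unequally (28 days against none) and has no branch for children withdrawn at Week 24. An unscheduled liver test after that visit is then lost to the plots and to the Appendix C window, although its Period 1 counterpart counts.

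The placement of the Week 24 tests depends on an undefined term. They are out of the Period 2 TE period if completion means the last-dose date and that dose was on the previous day. They are in it if completion means the visit date, with a possible second assignment to Part 2 for children who continue. In the worst case, assuming no Week 20 sample, none of the one post-dose Period 2 laboratory visit mapped in Appendix C would reach the plots, and with 1:1 sequences about half of the scheduled child-by-treatment records would be missing from them.

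The practical effect is mainly on the scatterplots and on unscheduled follow-up tests, within a safety analysis that SAP 9.4 makes descriptive. The documents do not say how many children are withdrawn at Week 24 or have repeat tests, so the number affected cannot be given. It is still worth correcting: in a small study one child's peak can shape the plot.

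**What to change.** In SAP 9.1:

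- Define treatment completion as a single date, and state that Week 24 pre-dose samples belong to Period 2.
- For children who do not enter Part 2, end the Period 2 TE period 28 days after treatment completion, matching Period 1.
- For children who do enter Part 2, end it immediately before the first Part 2 dose.

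In Appendix C, align the upper limit of the Period 2 laboratory window: Day 85 for children who do not enter Part 2, as in Period 1, and the Week 24 pre-dose sample for those who do.

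Check: with the tail, the Period 2 TE period ends on Day 84 or Day 85, so a Day 57 sample and a Day 60 repeat are both inside on either definition of completion. For children entering Part 2, the Week 24 sample falls in Period 2 only.

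While this section is open, the third Period 2 item should also be corrected: it refers to children who discontinued during Treatment Period 1, apparently carried over from the list above it.

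The cost is a few lines of text and a small programming change before database lock, with no new data. The downside is that the tail adds only unscheduled tests, so it may change few or no plotted points.

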**Table 3-2 Study VX15-770-123: Part 1 and Part 2**

		Part 1 Placebo-controlled Crossover Period a															
		Treatment Period 1 (Day 1 to Wk 8)				Wash-out				Treatment Period 2 (Wk 16 to Wk 24)				Part 2 Open-label Period a (Wk 24 to Wk 144)			
		Wk 4 (±3 days)	Wk 8 (±5 days)	Wk 8 (±5 days)	Wk 16 (±3 days)	Wk 20 (±3 days)	Wk 24 (±5 days)	Wk 36 (±2 wks)	Wk 48 (±2 wks)	Wk 60 (±2 wks)	Wk 72 (±2 wks)	Wk 84 (±2 wks)	Wk 96 (±2 wks)	Wk 108 (±2 wks)	Wk 120 (±2 wks)	Wk 132 (±2 wks)	Wk 144 (±2 wks)
Event/ Assessment	Day 1	X	X	X	X	X	X	X	X	X	X	X	X	X	X	X	X
Meal or snack at study center i		X	X		X	X	X	X	X	X	X	X	X	X	X	X	X
Study drug dosing at study visit i		X	X	X j	X	X	X k	X	X	X	X	X	X	X	X	X	X
Dispense study drug l		X	X		X	X	X	X	X	X	X	X	X	X	X	X	X
Study drug count		X	X	X	X	X	X	X	X	X	X	X	X	X	X	X	X
Adverse events																	
Continuous from signing of ICF through end of study participation																	

i Study drug (placebo or Kalydeco) will be administered from Day 1 to the dose before the planned Week 24 Visit. Study drug should be administered every 12 hours, with fat-containing food (see Section 10.2). At the scheduled visits indicated, this meal or snack will be provided at the clinic to subjects after all predose assessments have occurred. Although subjects will not be dosed with study drug at the Week 8 or Week 144 Visits, a meal or snack will be provided. All subjects will be treated with Kalydeco during Part 2.

j Study drug will not be administered at the Week 8 Visit of Treatment Period 1. The last dose of study drug in Treatment Period 1 is the dose of study drug before the Week 8 Visit.

k The first dose of Kalydeco in the Open-label Period will be administered at the Week 24 Visit. Kalydeco dosing will continue to the dose before the planned Week 144 Visit.

l Study drug will be assigned through an interactive voice or web response system.

**Table 3-3 Study VX15-770-123: Early Termination of Treatment Visit, Safety Follow-up Visit, and Follow-up Telephone Contact**

Event/Assessment	Early Termination of Treatment Visit a	Safety Follow-up Visit 4 weeks (±7 days) After Last Dose of Study Drug a	Follow-up Telephone Contact 4 weeks (±7 days) After the Week 144 Visit
Clinic visit	X	X	
Telephone Contact			X
Concomitant medications	X	X	
Concomitant treatments and procedures	X	X	
Height and weight	X	X	

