## 7. STUDY DESIGN

### 7.1 Overview of Study Design

This is a 2- part, randomized, double- blind, placebo- controlled, crossover study with a long-term open- label period. A schematic figure of the study design is presented in Appendix A.

In addition to the Screening Period (up to 4 weeks in duration), subject participation is anticipated to last approximately 148 weeks (2 Treatment Periods of 8 weeks each, Washout Period of 8 weeks, Open -label Period of 120 weeks, and Follow-up Telephone Contact approximately 4 weeks after last dose of study drug).

Subjects will be randomized 1:1 to receive 1 of 2 treatment sequences during Part 1:

- Sequence 1: ivacaftor in Treatment Period 1 → washout → placebo in Treatment Period 2
- Sequence 2: placebo in Treatment Period 1 → washout → ivacaftor in Treatment Period 2

This study includes:

- Screening Period: Day -28 through Day -1 relative to the first dose of study drug
- Part 1 Treatment Period 1 through Treatment Period 2

- Treatment Period 1: Day 1 (first dose of study drug) through Week 8
- 8-week Washout Period
- Treatment Period 2: Week 16 through Week 24
- Part 2 Open-label Period: Week 24 through Week 144 (the first dose of ivacaftor during the Open-label Period will be given after completion of assessments at the Week 24 Visit); the Week 24 Visit (Part 1) is also considered the first visit of the Open-label Period.
- Follow-up Telephone Contact (4 weeks [ $\pm 7$  days] after the last dose of study drug)

Subjects who prematurely discontinue study drug treatment will be required to complete the Early Termination of Treatment Visit, which is to be scheduled as soon as possible after it is decided that the subject will terminate study drug treatment. Subjects who prematurely discontinue study drug treatment will also be required to complete the Safety Follow-up Visit, approximately 4 weeks ( $\pm 7$  days) after their last dose of study drug. If the Early Termination of Treatment Visit occurs 3 weeks or later following the last dose of study drug, then the Early Termination of Treatment Visit will replace the Safety Follow-up Visit, and a separate Safety Follow-up Visit will not be required.

Subjects will continue to complete all other scheduled study visits for assessments of efficacy and other endpoints as detailed in the Schedule of Assessments. Subjects who discontinue study drug treatment during Part 1 will not be allowed to participate in Part 2 of the study.

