**Data Presentation:**

Where applicable and possible, data will be presented by ivacaftor dose group (50mg, 75mg and 150mg), placebo and overall ivacaftor dose group. For summary statistics, descriptive statistics will be presented for each visit and change from period baseline.

**Unscheduled Visits:** Unscheduled visit measurements will be included in the following:

- derivations of measurements at scheduled visits per specified visit windowing rules;
- derivations of baseline/last on-treatment measurements;
- derivations of the maximum/minimum on-treatment values and maximum/minimum changes from baseline values for safety analyses;
- data listings where appropriate.

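### By-visit laboratory summaries use the record nearest Day 57 with no priority for the scheduled visit and no regard to drug status, so an off-drug sample can replace an on-drug one

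*SAP*

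**What the plan says.** The Visit Windowing Rules in SAP 9.1 apply to scheduled and unscheduled visits alike. When several safety records fall in one window, "the record closest to the target day will be used, with the exception of the threshold analysis", for which the worst record is taken. On ties, "if there are multiple records within the same distance of the target day, the latest record will be used". For efficacy parameters the first choice differs: "the record at the scheduled visit will be used". Under Unscheduled Visits, SAP 9.1 confirms that unscheduled samples feed "derivations of measurements at scheduled visits per specified visit windowing rules".

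SAP Appendix C gives chemistry, hematology and liver function tests (LFTs) one post-baseline window per period, with target Day 57. The window is Days 2 to 85 in Period 1 and ["2, Date of Week 24 visit"] in Period 2.

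On dosing, Protocol Table 3-2 states: "Study drug will not be administered at the Week 8 Visit of Treatment Period 1". Protocol 8.1.2 likewise places the last Period 1 dose before that visit. For children who stop drug early, SAP 7.1 and Protocol 8.1.7 state: "Subjects will continue to complete all other scheduled study visits for assessments of efficacy and other endpoints". Protocol 11.5.2 requires LFTs at least every 4 weeks for children who meet the interruption or discontinuation criteria.

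SAP 9.4.2 summarizes values and changes from baseline by treatment group and time point, with box plots and mean plots for LFTs. It adds: "Abnormal hematology, chemistry, and LFT results will be summarized at each visit and also listed". None of these summaries is restricted to on-drug samples.

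**The concern.** In Period 1 the scheduled Week 8 sample follows the last dose directly, so it represents the end of treatment. Any later sample in that window is a washout sample. Under a nearest-to-target rule, a washout retest can become the Week 8 value even though the scheduled sample exists. After early stopping or interruption, an off-drug sample at a scheduled visit can likewise replace the last on-drug sample and be reported under that treatment.

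Such replacements do not occur at random. Repeat tests are ordered because a result was abnormal, and on average the repeat will be closer to normal. At stake are the by-visit means, changes from baseline, abnormality counts and plots, which form most of the treatment comparison for laboratory safety. With few children per column, one replaced record can move a mean visibly.

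**Working it through.** **Reproducing the plan's window.** Target day: 8 × 7 + 1 = 57. Upper limit in Period 1: 57 + 28 = 85, the target plus the 28-day tail of the treatment-emergent period in SAP 9.1. Both match Appendix C.

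**Inputs.** The Week 8 Visit tolerance of ±5 days (Protocol Table 3-2) allows visit days s = 52 to 62, which is 11 days. The selection and tie rules are those of SAP 9.1.

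**1. Sample drawn after the end-of-period visit.** A sample L days later displaces the scheduled one when |s + L − 57| ≤ |s − 57|. For s < 57 this reduces to L ≤ 2(57 − s). For s ≥ 57 it is never met.

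| Week 8 Visit day | Later sample days that displace it | Number |
|---|---|---|
| 52 | 53–62 | 10 |
| 53 | 54–61 | 8 |
| 54 | 55–60 | 6 |
| 55 | 56–59 | 4 |
| 56 | 57–58 | 2 |
| 57–62 | none | 0 |

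The Period 1 total is 10 + 8 + 6 + 4 + 2 = 30 day-pairs. By lag:
- L = 2: the condition is s ≤ 56, so 5 of 11 visit days (45%).
- L = 3: the condition is s ≤ 55, so 4 of 11 (36%).

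These lags match the 48 to 72 hours that Protocol 11.5.2 gives for repeating certain LFT elevations. In Period 2 the count is 0 whatever the visit day, because the window closes at the visit.

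**2. Sample drawn before a late visit (Days 58–62).** An earlier repeat nearer Day 57 wins in 1 + 3 + 5 + 7 + 9 = 25 day-pairs, in each period. Example in Period 2: samples on Days 52 and 55 and a visit on Day 62 have distances 5, 2 and 5, so Day 55 is used. If dosing continued, this repeat is on drug. The scheduled record is lost, but drug status is not the issue.

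**3. Early stop.** Suppose the last on-drug sample is on stop day d = 2 to 51 and an off-drug sample is drawn at the end-of-period visit on Day 52 to 62. The first is at least 57 − 51 = 6 days from target and the second at most 5. The off-drug sample is chosen in all 50 × 11 = 550 combinations, in each period. It lies more than 28 days after the last dose when d ≤ s − 29, which gives 22 + 23 + … + 32 = 297 of the 550.

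**4. Interruption.** Take an on-drug elevation on Day 30 and an off-drug repeat on Day 33. The distances are 27 and 24, so Day 33 is used if nothing later exists. Otherwise a Day 57 off-drug sample is used. The result is the same in both periods.

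**Illustration (all values assumed).** Eight children are in a column. Seven have ALT 0.7 × ULN. One has 6 × ULN at a Day 54 visit and 2 × ULN at a Day 57 retest. With the scheduled record, the mean is (6 + 7 × 0.7)/8 = 1.36 × ULN. Under the SAP rule it is (2 + 7 × 0.7)/8 = 0.86 × ULN.

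**The case against.** The strongest reply is that extremes are kept elsewhere. LFT threshold tables use the worst record, SAP 9.4.2 plots peak ALT and AST against peak bilirubin, and listings hold every value. SAP 9.1 lets unscheduled samples enter maximum and minimum on-treatment derivations. Protocol 12.3.5.2 promises a tabulation of maximum on-treatment results, and SAP 3.1 declares no departure from the protocol. This largely stands. A reader might infer that abnormal results vanish from the report; they do not. The remaining gap is that SAP 9.4.2 calls for threshold tables for LFTs only and specifies no maximum-value table for other laboratory tests, although Appendix E lists criteria for them.

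Second, the unequal windows have a plausible reason. Day 85 matches the treatment-emergent tail, and Period 2 must close at Week 24 because open-label ivacaftor starts then. That explains the window limits. It does not explain preferring a washout retest to an existing scheduled sample.

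Third, laboratory tests after early stopping are not certain for every child. Protocol 11.5.2 requires routine LFTs while on drug, and the instruction to continue visits refers to efficacy and other endpoints. Later samples are required only for children who meet the LFT criteria and are possible for the rest. The early-termination sample is itself often off drug. Safety Follow-up samples keep their nominal visit and do not compete. All of this stands and limits the reach of the point.

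Finally, safety is descriptive, with no testing, in a small terminated study. That lowers the weight but does not remove the defect.

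**Conclusion.** The concern holds as a minor point. The safety rule lets an off-drug sample replace an on-drug one in the by-visit laboratory summaries, with an expected pull toward normal. Post-visit retests do this in Period 1 only, and only for visits on Days 52 to 56. Off-drug samples after early stopping or interruption do it in both periods.

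The 5 of 11 and 4 of 11 are shares of allowed visit days, given that a retest occurs at that lag. The documents give no retest frequency and no distribution of visit days, so no probability of displacement follows. The direction rests on retests being prompted by abnormal results; an individual retest may be higher.

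Two stronger readings are tempting. One is that displacement as a whole is a Period 1 problem. Steps 2 to 4 of the working show that it is not. The other is that the different window limits bias the ivacaftor–placebo contrast. Under 1:1 randomization both treatments are given in Period 1, so the rule acts on both columns, and the documents do not show a net bias for either.

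**What to change.** In SAP 9.1, for by-visit safety summaries in both periods:
- Use the record at the scheduled visit when one exists and the child was on study drug up to that visit.
- If drug was stopped or interrupted earlier, use the last sample taken on drug or, if there is none after baseline, the early-termination sample.
- Show later off-drug samples in a separate off-treatment row.
- Keep the worst-record rule for the threshold analysis.

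The cost is a few lines of SAP text and an on-drug flag. The exposure and compliance derivations in SAP 9.2.5 and 9.2.6 already need dose dates and interruption days, so no new data are required. SAP section 4 places finalization before database lock. The small downside is that off-drug values of children who stopped early leave the Week 8 row; they remain in the off-treatment row and the listings.
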